## RESEARCH OBJECTIVES AND SPECIFIC AIMS

Several observational and randomized controlled trials (RCT) have reported that inpatient hyperglycemia is associated with an increased risk of complications and mortality (1-5). Several interventional trials have shown that treatment of hyperglycemia in critically ill and non-ICU patients is associated with shorter length of hospital stay and lower rates of hospital complications. Several prospective, randomized trials in general medicine and surgical patients with type 2 diabetes (T2DM) have shown that treatment with basal bolus insulin regimen results in better glycemic control and lower rate of hospital complications compared to treatment with sliding scale regular insulin in patients (4; 6-8). Indeed, basal bolus regimen is recommended in clinical guidelines by multiple professional societies (9; 10) for treatment of inpatient hyperglycemia and T2DM in non-ICU patients.

While basal bolus regimens are recommended, they consist of multiple daily injections. In addition, they require correction of blood glucose (BG) levels with supplemental (corrective) doses of insulin based on BG levels (4; 6; 7; 11; 12). Data from our group has shown that simplified regimens such as a basal-plus regimen may be just as effective for glycemic control as a basal bolus regimen (11). Additionally, recent data from one of our RCTs showed that corrective doses of insulin at bedtime for mild to moderate hyperglycemia, a standard of care practice, may not be necessary (13). Glycemic control, rates of hypoglycemia or total daily dose (TDD) of insulin did not differ whether corrective doses of insulin were given or not for bedtime hyperglycemia. Similar to this trial, several trials from our group with different basal bolus regimens show that the amount of supplemental insulin per day is between 5-9 units/day (See Table 1). It is possible that the use of insulin supplements may increase the risk of hypoglycemic events, an independent marker of mortality (14). These small amounts of daily supplemental insulin requirements raise the question of whether corrective doses of insulin before meals and bedtime are beneficial in inpatient treatment for T2DM.

Currently, no RCTs have prospectively evaluated the need for corrective doses of insulin as part of a basal bolus regimen in the inpatient setting. We propose to study the safety and efficacy of the standard practice of correcting mild to moderate hyperglycemia (BG 140-260 mg/dL) before meals and bedtime in patients treated with basal bolus insulin regimen. A glucose > 260 mg/dL was picked arbitrarily. **We hypothesize that correction of mild-moderate hyperglycemia with rapid-acting insulin analogs (standard of care) will not improve glycemic control or complication rates and may increase the risk of hypoglycemia.** If supplemental insulin is not necessary to correct mild-moderate hyperglycemia, inpatient management of hyperglycemia in patients with T2DM may be simplified, may reduce the risk of hypoglycemia and save costs.

**Specific Aim: To test whether correction of mild-moderate hyperglycemia (BG > 140 mg/dL) with supplemental doses of rapid-acting insulin analogs improves glycemic control, complication rates, and rates of hypoglycemia in hospitalized patients with type 2 diabetes treated with basal bolus insulin regimen.** Patients with T2DM admitted to the hospital receiving basal bolus therapy will be randomized to receive insulin correction before meals and at bedtime for BG >140 mg/dL, while others will be followed without insulin supplementation except for severe hyperglycemia (BG > 260 mg/dL).

**Table 1:** Total and Supplemental Insulin needs in Basal Bolus Arm of RCT

Trial	Number	Mean TDD Insulin	Mean daily SSI
RABBIT 2D (7)	65	42 units/day	5 units/day
RABBIT 2 Surgery (6)	104	33 units/day	9 units/day
POC Study	206	42 units/day	6 units/day
Basal-Plus (11)	144	32 units/day	7 units/day
DEAN Trial (12)	67	57 units/day	8 units/day

## II. BACKGROUND AND CURRENT STATUS OF WORK IN THE FIELD.

**Inpatient Glycemic Control in non-ICU setting.** A large body of evidence suggests that in hospitalized patients with and without diabetes, the presence of hyperglycemia is associated with increased risk of complications and death (2-5; 15-20). Prospective RCTs in critical care patients have shown that aggressive glycemic control reduces short- and long-term mortality, multi-organ failure, systemic infections, and length of hospital and ICU stay [7, 9-11]. Similar complication reductions has been shown in patients admitted to general medicine and surgery services as well. In the non-ICU setting, practice guidelines for the management of hyperglycemia in patients with T2DM favor the use of physiologic (basal-nutritional-correction dose) insulin regimens over sliding scale regular insulin (SSRI) (4; 5). Several RCTs have shown that a basal bolus regimen improves glycemic control and reduces hospital complications in general medicine and surgery patients with T2DM (5-7; 21; 22).

Treatment with basal insulin glargine alone or in combination with rapid-acting insulin analogs before meals (basal bolus regimen) result in fairly constant BG values during the day (see preliminary data below). We have shown that with the exception of a small and non-significant rise in BG concentration before lunch (noontime), treatment with glargine insulin allows 24 hours of BG control with low rates of hypoglycemia, severe hyperglycemia and minimal requirement of insulin supplements (~5-9 U/day) (6; 7). In particular, our data indicate that BG concentration remains relatively constant during the evening with a low rate of severe hyperglycemia (0.1% of BG >400 mg/dl) despite minimal use of insulin supplements (see preliminary data). This small dose of supplemental insulin used in our previous studies raises the question of its necessity as part of a basal bolus regimen.

Several RCT have shown that hypoglycemia occurs in 12% and 33% of general medicine and surgery patients treated with basal bolus insulin regimens, respectively (6; 7; 11; 12). In the RABBIT-surgery trial (6), general surgery patients were treated with a total insulin dose of 0.5 unit/kg/day, given half as glargine once daily and half as glulisine before meals. A total of 17% of patients had a BG <70 mg/dL and 4% had a value <40 mg/dL. More recently, the Basal Plus trial (11) reported that 12% and 5% of patients treated with basal bolus with glargine and glulisine or with basal plus correction (supplements), respectively, had a BG <70 mg/dL and

only 1% had a BG <40 mg/dL. In the DEAN trial (12), a basal-bolus regimen using detemir and aspart vs. NPH and regular insulin reported that ~one-third of patients had a BG < 60 mg/dl (12). Minimizing hypoglycemic events is of major importance in hospitalized patients because it has been shown to be an independent risk factor of poor outcome (23-25). It is not known, however, if the use of insulin supplements may have an impact on the overall rate of hypoglycemia in patients treated with basal bolus insulin regimen.

**Significance and Innovation:** Inpatient hyperglycemia is reported in up to 30% of general medicine and surgical patients. Our data indicate that in patients treated with basal (glargine or detemir) insulin, BG values remain relatively flat, without significant differences in use of insulin supplements or rate of hypoglycemia (6; 7). Moreover, in a recent study, we showed that there were no differences in glycemic control or hypoglycemic episodes with or without the correction of mild to moderate hyperglycemia with supplemental insulin at bedtime. All of our RCTs showed that supplemental insulin needs are small and are only between 6-9 units/day. However, no previous studies have determined if the use of supplemental insulin to correct hyperglycemia results in a change in glycemic control or hypoglycemia rates. It is possible that avoiding correction of mild to moderate hyperglycemia with supplemental insulin may result in lower rates of hypoglycemia and significant cost in hospitalized patients with T2DM treated with basal insulin analogs. *Accordingly, the proposed pilot study will provide novel and clinically useful information by determining if insulin supplementation will improve glycemic control and prevent hypoglycemia in insulin treated patients with T2DM. If insulin supplementation is not necessary for glycemic control, this may result in simplified insulin regimens, potentially reduce hypoglycemic episodes and save costs.*

[figure not shown]
### Preliminary Data:

Our research team recently reported the results of four prospective, multi-center RCT comparing the efficacy and safety of different insulin regimens in T2DM patients admitted to general medicine and surgical services (6; 7; 11; 12). We have shown that a basal bolus regimen results in improved glycemic control compared to SSRI. In particular, these trials showed that the amount of supplemental insulin needed is very low.

In the Rabbit trial (Fig 1), 130 nonsurgical insulin naïve patients were randomized to receive glargine once daily and glulisine before meals (basal bolus) or SSRI before meals and at bedtime. Of these, 65 patients treated with glargine/glulisine (basal bolus) had greater improvement in BG control than SSRI with minimal risk of patients with

[figure not shown]
Fig 1

Mean Blood Glucose Levels During Basal Bolus and SSRI

hypoglycemic events (3% of patients in each group had a BG < 60 mg/dL). A BG target of < 140 mg/dL was achieved in 66% of patients treated with glargine and glulisine whereas only 38% of those treated with SSRI achieved target glycemia. In this study, patients in the basal bolus arm required total insulin of 42 units/day. Of this, only 5 units/day were needed as supplemental insulin (Table 1).

In the DEAN trial (12), 130 patients with T2DM were treated with detemir once daily and aspart before meals (n=67) or with a split-mixed regimen of NPH and regular insulin twice daily (n=63) (Figure 2). Both regimens resulted in equivalent glycemic control and a similar rate of hypoglycemic events. A BG target <140 mg/dL before meals was achieved in 45% of patients in the detemir/aspart group and in 48% in the NPH/regular group. The TDD of insulin in the detemir arm was 57 units/day and of that the supplemental dose was only 8 units/day.

In the Rabbit-Surgery trial (Figure 3), 211 general non-cardiac surgery patients with T2DM were randomized to a basal bolus regimen with glargine once daily and glulisine before meals (n=104) or to SSRI before meals (n=107). Study outcomes included differences in daily BG levels and a composite of hospital complications including postoperative wound infection, pneumonia, respiratory failure, acute renal failure, and bacteremia. The mean daily glucose after the 1st day of BB and SSRI was 145±32 mg/dl and 172±47 mg/dl, respectively, p<0.01. BG readings <140 mg/dl were recorded in 55% of patients in basal bolus and 31% in the SSRI group, p<0.001. There were reductions with basal bolus as compared with SSRI in the composite outcome (24.3% and 8.6%, OR: 3.39 (95% CI: 1.50-7.65); p=0.003). We concluded that treatment with basal improved glycemic control and reduced hospital complications compared to SSRI in surgery patients with T2DM. The TDD of insulin in the basal bolus group was 33 units daily with 9 units/day of supplemental insulin. The basal bolus group in this study received more supplemental insulin than patients in the basal bolus arms of our other RCTs. This is likely because ~ 30% of patients in the Rabbit-Surgery trial underwent abdominal surgery and were likely

Figure 3. Postoperative Complications

[figure not shown]

Figure 4. Basal Bolus vs Basal Plus

[figure not shown]
[figure not shown]

Figure 5. BG before meals and at bedtime

[figure not shown]
[figure not shown]
NPO. These patients did not receive prandial insulin and therefore the supplemental dose may have been higher.

In the Basal Plus trial (11), we compared the effect of a daily dose of glargine with correction doses of glulisine to a standard basal bolus regimen in 300 medical and surgical patients with T2DM. We observed similar mean daily BG (Figure 4), pre-meal glucoses (Figure 5) and hypoglycemic events. There were no differences in length of hospital stay or hospital complications between patients treated with basal plus and basal bolus insulin regimen. These results indicate that a simple regimen of a daily basal dose of glargine plus correction doses with glulisine before meals (as needed) is an alternative to basal bolus insulin and results in similar glycemic control and hypoglycemia in general medicine and surgery patients with T2DM. In the basal bolus arm of the study, TDD of insulin was 32 units/day and of this only 7 units/day was given as supplemental dose.

In a recently completed study (POC) (13), we found that not correcting mild to moderate hyperglycemia at bedtime did not change fasting daily glucose levels (Figure 6). Further, there were no changes in mean daily glucose, pre-meal glucose or hypoglycemic events (Figure 7). In this study, TDD of insulin was 42 units/day. Of this, only 6 units/day was required as a supplemental dose.

**Frequency of hypoglycemia and hyperglycemia during basal insulin treatment.** The frequency of mild hypoglycemia (BG<70 mg/dl) and severe hypoglycemia (BG<40 mg/dl) at bedtime among 2,377 patients recruited in different randomized control trials conducted by our research team is less than 1.5% and 0.5%, respectively. The frequency of hypoglycemia is low in comparison to patients treated with sulfonylureas (26). Similarly, the frequency of severe hyperglycemia (BG>400 mg/dl) is remarkably low (0.08%) among insulin treated patients with T2DM (6; 7).

*In summary*, during the past decade our research group has provided novel and important information to guide health care providers in inpatient management of patients with hyperglycemia and diabetes. Our preliminary data indicate that the use of basal insulin alone or in combination with rapid-acting insulin analogs (basal bolus regimen) in non-ICU patients with T2DM improves glycemic control and reduces the rate of hypoglycemia. In addition, our studies

have shown that BG values remain relatively constant during the day and that the need for supplemental insulin is low in comparison to the TDD of insulin required.

#### **IV. Experimental Plan:**

Specific Aim: To test whether correction of mild-moderate hyperglycemia (140-260 mg/dL) with supplemental doses of rapid-acting insulin analogs improves glycemic control, complication rates, and rates of hypoglycemia in patient with type 2 diabetes treated with basal bolus insulin regimen.

##### **IV.a. Study Design and Methods:**

**A total of 250 general medicine and surgery patients with T2DM treated with basal bolus insulin regimen will be included in this pilot RCT. Half of the patients will be randomized to receive insulin supplements before meals and at bedtime for BG >140 mg/dL, while the other half will be followed without insulin supplementation except for severe hyperglycemia (BG > 260 mg/dL).**

##### **IV.b. Primary and Secondary Outcomes:**

The primary outcome of the study is to compare differences in mean daily BG levels between patients receiving insulin supplementation for correction of hyperglycemia (BG > 140 mg/dL) compared to those without insulin supplementation except for correction of severe hyperglycemia (BG > 260 mg/dL).

Secondary outcomes include differences between treatment groups in any of the following measures: 1) mean BG before meals, bedtime and 3 AM; 2) number of BG within target; 3) number of hypoglycemia (BG < 70 mg/dl); hyperglycemia (BG > 260 mg/dL during the day or BG>350 mg/dl at bedtime); 4) daily dose of insulin; 5) length of hospital stay and mortality; 6) hospital complications (nosocomial infections, pneumonia, bacteremia, respiratory failure, and acute kidney injury [rise of serum creatinine >0.5 mg/dL (or 50%) of baseline value]), 7) hypoglycemia symptom assessment in both groups.

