## **VI. CLINICAL MANAGEMENT GUIDELINES**

**V.I.a. Treatment of Hypoglycemia.** Hypoglycemia, defined as a BG level < 70 mg/dL will be treated following standard hypoglycemia protocols available at our institutions (6; 7; 29).

**V.I.b. Assessment and Monitoring of Hospital Complications and Mortality.** The research team will follow patients daily in order to determine presence of infectious and non-infectious complications. Nosocomial infections will be diagnosed based on standardized CDC criteria (30).

**VII. Data Analysis.** The primary endpoint of this study is mean fasting BG concentration between treatment groups. We set the equivalence margin in our non-inferiority hypothesis for comparing treatment effect as 18 mg/dL (1 mmol/l). Based on previous studies (6; 7), we anticipate a standard deviation of mean fasting BG~50 mg/dL. With a one-sided, two-sample t-test, 123 subjects would be required for each group to achieve 80% power to detect non-inferiority. Here we conservatively set the significance level as 0.025 to ensure sufficient power when a two-sided test is used for the primary outcome, we will perform cross-sectional analyses using one-way ANOVA or linear models, followed by repeated measures ANOVA or linear models to estimate difference between treatment groups while simultaneously examining mean fasting BG across multiple days during treatment. Similar analyses will be conducted for continuous secondary outcomes. Chi-square tests (or Fisher's Exact test), Logistic regression, and Poisson regression will be conducted to analyzed discrete secondary outcomes. A p-value of <0.05 is considered significant. We expect a very low attrition rate in the proposed study. Therefore, a total of 250

patients (125 patients per group) will be recruited in this pilot study. The proposed methods will be implemented by SAS (v9.2).

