### **VIII. Protection against risks.**

**VIII.a. Hypoglycemia.** We expect that <10% of subjects will experience episodes of hypoglycemia. To minimize the risk, outpatient dose of insulin will be reduced by 20% on admission; and insulin naïve patients  $\geq 70$  years of age and/or with an eGFR  $< 60$  will be started at a TDD of 0.3 U/kg/day.

**VIII.b. Severe hyperglycemia.** Patients with persistent hyperglycemia ( $\geq 3$  consecutive BG readings  $> 260$  mg/dL or a mean daily BG  $\geq 260$  mg/dL) after the 1st day of treatment will be considered as treatment failure and will be switched to continuous insulin infusion if needed. Patients randomized to group 1 will receive insulin supplements for BG  $> 140$  mg/dL. Those randomized to group 2 will receive insulin supplements only when BG  $> 260$  mg/dL. We anticipate that less than 1% of patients will experience severe hyperglycemic episodes (BG  $> 350$  mg/dL).

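### The primary glucose mean has no stated start, so readings taken before the first study insulin dose may be averaged in, which favours non-inferiority

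*Combined protocol and SAP*

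**What the plan says.** Section IV.b (Primary and Secondary Outcomes) sets the primary outcome as a comparison of mean daily BG: the study is to "compare differences in mean daily BG levels between patients receiving insulin supplementation for correction of hyperglycemia", against patients supplemented only above 260 mg/dL. It names no first day, no last day and no set of readings.

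Section VII (Data Analysis) names a different variable: "The primary endpoint of this study is mean fasting BG concentration between treatment groups". The 18 mg/dL margin, the SD and the sample size are all attached to that fasting mean. The analysis is one-way ANOVA or linear models, followed by repeated-measures versions over several treatment days. No first day is given and no baseline covariate is named.

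A first-day exclusion appears in two other places. The Preliminary Data section reports the group's surgery trial this way: "The mean daily glucose after the 1st day of BB and SSRI". Section VIII.b applies its persistent-hyperglycaemia rule only after the first day of treatment; patients who meet it "will be considered as treatment failure and will be switched to continuous insulin infusion if needed". Neither passage defines this trial's primary outcome.

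The glucose monitoring paragraphs for both groups require every reading to be recorded, so entry-day values will be in the data.

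**The concern.** A reading taken before the first study insulin dose has the same expected value in both arms because of randomisation. If it enters the average, it contributes a zero difference and pulls the estimated treatment effect toward zero.

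In a superiority trial that costs power. Here the aim is to show that withholding correction is not worse by 18 mg/dL or more, so the same pull makes it easier for an inferior arm to pass. With the window unstated, the choice of readings could also be made after the data are seen.

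**Working it through.** **Inputs from Section VII.** Margin 18 mg/dL; "we anticipate a standard deviation of mean fasting BG~50 mg/dL"; one-sided alpha 0.025 ("Here we conservatively set the significance level as 0.025"); power 80%; 125 recruited per group. **From the monitoring paragraphs:** 4 or 5 scheduled readings a day (three pre-meal and bedtime, with or without 3 AM).

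**Assumptions.** The documents give no number of days averaged, so D = 3, 4, 5 or 7 is assumed. Readings are equally weighted, the true difference is exactly 18 mg/dL on every affected reading, and the SD of the patient mean stays at 50 whichever readings are counted. That SD is stated for fasting BG and is borrowed for daily BG.

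**Step 1: the plan's own figure.** The plan states: "With a one-sided, two-sample t-test, 123 subjects would be required for each group". The normal approximation gives n = 2 × (1.96 + 0.8416)² × 50² / 18² = 121.1, so 122 per group. The noncentral t calculation gives 123 (power 0.803; at 122 it is 0.7997). At 125 per group, power is 0.81. The stated figure reproduces. It assumes a true difference of zero, and diluting zero leaves zero, so the sample size is not affected.

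**Step 2: standard error.** SE = 50 × √(2/125) = 6.32 mg/dL.

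**Step 3: dilution.** Let w be the share of the average made up of unaffected readings. Then:

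- expected difference = 18 × (1 − w)
- P(declare non-inferiority) = Φ(18w / 6.32 − 1.96)

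With w = 0 this is 2.5%, the nominal level. With r readings a day, one pre-dose reading gives w = 1/(rD), half a day gives w = 1/(2D), and a whole day gives w = 1/D.

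| Days averaged | One reading, r = 4 | One reading, r = 5 | Half a day | Whole day: expected difference | Whole day: error |
|---|---|---|---|---|---|
| 3 | 4.3% | 3.8% | 6.9% | 12.0 mg/dL | 15.6% |
| 4 | 3.7% | 3.5% | 5.4% | 13.5 mg/dL | 10.6% |
| 5 | 3.5% | 3.2% | 4.7% | 14.4 mg/dL | 8.2% |
| 7 | 3.2% | 3.0% | 3.9% | 15.4 mg/dL | 6.0% |

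Worked example, 3 days with one whole zero-effect day: w = 1/3, the expected difference is 18 × 2/3 = 12.0, and Φ(6/6.32 − 1.96) = Φ(−1.01) = 15.6%.

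**Step 4: the fasting version.** A fasting mean has one value a day. If a pre-dose fasting value is one of D values, then w = 1/D and the whole-day column applies, with SD 50 as stated rather than borrowed. If no pre-dose fasting value is counted, this dilution does not arise.

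**The case against.** A reader might infer that the plan does count the entry day and that day-1 readings are equal in the two arms by design. The documents do not support either inference.

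- **The text is silent, not inclusive.** Section VII speaks of days of treatment, which does not suggest pre-treatment readings. The surgery trial's after-first-day reporting fits an intention to exclude day 1 at least as well as one to include it. Equally, nothing writes such an exclusion down here, and Section VIII.b had to state its own.
- **Later day-1 readings can differ.** Group 1's pre-meal scale gives supplements above 140 mg/dL, while Group 2's gives none up to 260. The arms can separate from the first pre-meal correction. A whole zero-effect day is therefore an upper bound for a daily mean, and only pre-dose readings are certain to carry no effect.
- **A strict day-2 start is debatable.** Both groups raise basal insulin daily when BG is above target. That could narrow the difference on later days, in which case dropping all of day 1 would itself shrink the contrast. The documents do not settle this.
- **The margin belongs to fasting BG.** Section IV.b contains no non-inferiority test. Applying 18 mg/dL and SD 50 to mean daily BG is a borrowing.
- **A smaller SD would give larger figures but is not a sound basis.** The 32 mg/dL in the Preliminary Data comes from one arm of a surgery-only trial whose other arm had 47, and both were measured after day 1.

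These objections stand, and they limit the size of the problem. They do not supply the missing start, and for pre-dose readings the direction of the bias is not in doubt.

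**Conclusion.** The point holds in a limited form. No section defines where the primary glucose average begins, and none excludes the qualifying BG or other pre-dose readings. If counted, they move the result toward non-inferiority.

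For a daily mean, one pre-dose reading raises the one-sided error from 2.5% to about 3-4%. The 16%, 11%, 8% and 6% figures are ceilings for a daily mean over an assumed 3, 4, 5 or 7 days, because they need a whole day without effect. They would apply directly to a fasting mean only if a pre-dose fasting value were one of the averaged values. All figures assume a true difference of 18 mg/dL on the remaining readings, equal weights, SD 50 and 125 per group. If pre-dose readings are excluded, the error is 2.5%.

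It is worth correcting because the bias runs in the anti-conservative direction and costs almost nothing to prevent.

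**What to change.** 1. Reconcile Section IV.b (mean daily BG) with Section VII (mean fasting BG), and state which one carries the 18 mg/dL margin and the SD.
2. Define the primary mean as the scheduled readings (of the chosen type) after the first study insulin dose and up to the end of study treatment. Exclude the qualifying BG and every other pre-dose reading.
3. Replace the unadjusted one-way ANOVA with a linear model that has randomisation BG as a covariate. Section VII already allows linear models, and this BG is already used for eligibility and starting dose. Take the covariate from the same reading in both groups, since Group 2's starting-dose text also refers to admission or mean BG. The adjustment improves precision; it is step 2 that removes the dilution.
4. Report the mean after the first day, the surgery trial's convention, as a sensitivity analysis.

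The cost is a few sentences, with no new data and no change to the sample size. The small downside is that patients with no reading in the window have no primary value, and they must be counted and reported by arm.

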**BEDTIME. Give half of Supplemental Sliding Scale Insulin.**

Blood Glucose (mg/dL)	Sensitive	Usual	Resistant
<221	0	0	0
221-260	1	2	4
261-300	2	3	5
301-350	3	4	6
351-400	4	5	7
> 400	5	6	8

The patient's inpatient primary medical or surgical team may change insulin dose at their discretion in the presence of hypoglycemia (BG <70 mg/dL) or severe hyperglycemia (BG >350 mg/dL). In addition, the attending and/or study physician may consider using the total supplemental insulin dose, patient's nutritional intake, and results of BG testing to adjust insulin regimen.

**Blood glucose monitoring.** BG will be measured before each meal, at bedtime and/or 3 AM (or every 6 hours if a patient is not eating) using a glucose meter. In addition, blood glucose will be measured at any time if a patient experiences symptoms of hypoglycemia or if requested by the treating physician. The nursing staff or a research team staff will record all glucose readings in the hospital's blood glucose flow-sheet (electronic chart).

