**IV.f. Inpatient Hypoglycemia Management:**

For blood glucose < 70 mg/dL, follow hypoglycemia orders below:

- If patient is alert and can tolerate oral intake, give 20 grams of fast-acting carbohydrate (6 oz. fruit juice or regular soda, crackers).
- If patient not alert and CANNOT tolerate oral intake, give 1 ampule (50 mL) of D50.
- Check finger-stick BG q 15 minutes and repeat above treatment until BG > 100 mg/dL.
- Once BG > 100 mg/dL, repeat finger-stick BG 1 hour later and treat as follows:
  - If BG < 70 mg/dL, call MD and follow Hypoglycemia Orders (above)
  - If BG 70 – 100 mg/dL, give snack/scheduled meal and recheck BG q 1 hr until BG > 100 mg/dL.
  - If BG > 100, no further treatment needed.

**IV.g. Treatment recommendations at discharge.** Treatment of diabetes at discharge will not be part of the current research proposal; however, the following guide based on admission HbA1c will be shared with primary team to help guiding outpatient insulin therapy:

- **Admission A1C < 7% prior to admission:**
  - Discharge on same pharmacologic regimen (oral agents, insulin therapy).
  - Assure there are no contraindications to oral agents (i.e., TZDs and heart failure; metformin and renal failure).
- **Admission A1C between 7% and 10% prior to admission:**
  - Discharge on once daily basal insulin (glargine or detemir) insulin.
  - If no contraindications to oral agents restart oral agents in addition to basal insulin (glargine or detemir) at 50% to 80% of total daily hospital dose.
  - Patients not to be treated with oral agents should be instructed to continue taking 100% of inpatient daily dose of glargine (as monotherapy).
- **Admission A1C ≥ 10% prior to admission:**
  - Discharge on basal bolus regimen at same inpatient total daily insulin dose.
    - Basal insulin (glargine or detemir) once daily, at the same time of the day.
    - Rapid-acting insulin (aspart/lispro) before meals.
  - Alternative: If no contraindications to oral agents (i.e., TZDs and heart failure; metformin and renal failure) restart oral agents in addition to glargine or detemir once daily at 80% of total daily hospital dose.

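### Secondary outcomes 2 and 3 are undivided counts over stays of unequal length, with no exposure offset, over-dispersion allowance or episode rule, so count tests can give false-positive results

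*Combined protocol and SAP*

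**What the plan says.** Section IV.b lists among the secondary outcomes "2) number of BG within target; 3) number of hypoglycemia (BG < 70 mg/dl"; the same item 3 adds hyperglycemia. It gives no denominator, observation window or rule for what makes one event. Item 5 is "5) length of hospital stay and mortality", so the length of observation varies between patients and is itself an outcome.

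Section VII (Data Analysis) names chi-square or Fisher tests and then "Logistic regression, and Poisson regression will be conducted to analyzed discrete secondary outcomes". It mentions no exposure term, no over-dispersion and no clustering of readings within a patient for these outcomes.

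On testing, section IV.f orders after a BG below 70 mg/dL: "Check finger-stick BG q 15 minutes and repeat above treatment until BG > 100 mg/dL", and then "Once BG > 100 mg/dL, repeat finger-stick BG 1 hour later and treat as follows". The monitoring paragraphs for both groups add that "blood glucose will be measured at any time if a patient experiences symptoms of hypoglycemia or if requested by the treating physician", and "The nursing staff or a research team staff will record all glucose readings". Nothing excludes repeat or unscheduled readings from the outcomes or merges them into one event.

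Scheduled testing is worded differently by arm. The Group 1 paragraph allows bedtime, 3 AM or both (4 or 5 tests a day with the three pre-meal tests). The Group 2 paragraph calls for both (5 a day).

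**The concern.** A count without a denominator mixes how well glucose was controlled with how long and how often it was measured. A patient who stays twice as long collects about twice as many in-target readings and twice as many low ones at identical control. The aim in section IV speaks of rates of hypoglycemia, but no rate is defined in the outcomes or the analysis.

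An ordinary Poisson model assumes that the variance of the counts equals their mean. Unequal stays break that assumption, and so do low readings that come in runs because each one triggers more tests. Standard errors are then too small and p-values too low. Hypoglycemia is the harm that the trial's hypothesis singles out, so a spurious difference there, or one hidden by unequal testing, would affect the main safety message.

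**Working it through.** **The plan's own figure.** Section VII gives 123 per group (margin 18 mg/dL, SD 50 mg/dL, one-sided 0.025, power 80%). Normal formula: 2 × 50² × (1.960 + 0.842)² / 18² = 121.1, so 122; the t-based version gives 123. It reproduces. It concerns mean fasting BG and does not size the count outcomes.

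**Inputs for the counts.** From the plan: 125 per arm, and 4 or 5 scheduled tests a day. Assumed, because the documents give no figures: mean stay 5 days, 50% of readings in target, 1.5% of scheduled readings starting a low episode, and a 10% to 50% chance that each recheck is still below 70 mg/dL.

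**Counts at equal control.**
- 4-day stay: 4 × 4 × 0.5 = 8 in-target readings. 6-day stay: 6 × 4 × 0.5 = 12. Ratio 1.5.
- 5 tests a day against 4: ratio 5/4 = 1.25.
- Low readings per episode, 1/(1 − q): 1.11 at q = 0.10, 1.67 at q = 0.40, 2.0 at q = 0.50.

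**Over-dispersion of in-target counts, balanced arms.** With p = 0.5 and 4 readings a day, variance/mean = (1 − p) + p × 4 × Var(stay)/Mean(stay).
- Poisson-distributed stays (variance 5): 0.5 + 0.5 × 4 × 5/5 = 2.5. Actual size of a nominal 5% test = P(|Z| > 1.96/√2.5 = 1.24) = about 21%.
- More dispersed stays (1 day plus a negative binomial with mean 4 and shape 2; variance 4 + 4²/2 = 12): 0.5 + 0.5 × 4 × 12/5 = 5.3. Actual size = P(|Z| > 1.96/√5.3 = 0.85) = about 39%.

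**Simulation.** 2,000 null trials, more dispersed stays, equal probability per reading in both arms. Offset is log(readings):

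| In-target counts | Poisson, no offset | Offset + robust variance |
|---|---|---|
| Same stay, same testing | 38% | 6% |
| One arm's mean stay 6 days | 87% | 5% |
| One arm tested 5 times a day, the other 4 | 95% | 6% |

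A separate simulation gave 21% with Poisson-distributed stays.

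| Low readings, balanced arms | No offset | Offset only | Offset + robust variance |
|---|---|---|---|
| Rechecks not counted | 6% | 5% | 5% |
| Rechecks counted, q = 0.40 | 23% | 21% | 6% |

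For low readings an offset alone does not cure the effect of re-testing; an episode rule or a robust variance is also needed.

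**Effect on mean BG.** Take an assumed day with scheduled readings 160, 160, 160 and 60: mean 540/4 = 135. Adding rechecks 65, 80, 105 and 110: 900/8 = 112.5, a fall of 22.5 mg/dL on that day. With one such day in a 5-day stay, the patient's mean falls by 22.5/5 = 4.5. If 10% of patients are affected (section VIII.a expects fewer than 10% to have hypoglycemia) the arm mean moves by 0.45 mg/dL; at 15%, by about 0.7.

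**The case against.** The strongest reply is that raw counting is inferred from silence. Elsewhere the protocol speaks of rates and of percentages of patients. Chi-square and logistic regression suit a yes/no outcome per patient, and Poisson regression can carry an offset that section VII neither states nor rules out. Nothing says that rechecks will be counted. This stands as far as intent goes. But the outcomes are worded as numbers, all readings are recorded, and an analyst who follows the text has no instruction that prevents a raw-count comparison.

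Second, randomization balances stay length in expectation, and the Basal Plus trial described in the preliminary data found no difference in stay. Rechecks follow the same rule in both arms, so if episodes yield similar numbers of low readings the ratio of counts is preserved. This also stands. A reader might infer that the counts are biased by arm; the documents do not show that. What balance leaves untouched is the inflated false-positive rate, which the calculation finds with equal stays and equal testing.

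Third, a reader might infer that all glucose outcomes are affected, the primary one included. They are not. IV.b says "The primary outcome of the study is to compare differences in mean daily BG levels", and secondary outcome 1 is also a set of means. The 22.5 mg/dL shift belongs to one constructed patient-day and cannot be set against an 18 mg/dL margin for arm means. At arm level the shift is under 1 mg/dL, and the difference between arms is smaller if both arms have such days.

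**Conclusion.** The point holds for secondary outcomes 2 and 3 only. As written, the plan allows counts that depend on days observed and on re-testing to be compared by tests that ignore both. With balanced arms the consequence is a false-positive rate of about 21% to 38% for in-target counts, and about 23% for low readings when rechecks are counted, against a nominal 5%. These sizes rest on the assumed stays, in-target share, episode rate and recheck probability; less variable stays or fewer repeat lows would make them smaller. Systematic bias is possible if stay or testing frequency differs by arm. The different 3 AM wording permits the latter, but neither is demonstrated. No material bias in the primary outcome is shown. The change should be made before analysis.

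**What to change.** **Section IV.b, item 2.** Use each patient's percentage of scheduled readings in target, compared between arms as one value per patient. State the target numerically: section IV.c gives below 140 mg/dL and section IV.d gives 100 to 140 mg/dL, and these must be reconciled.

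**Section IV.b, item 3.** Report hypoglycemic episodes per patient-day, counting all readings from the first BG below 70 mg/dL until BG exceeds 100 mg/dL (the end point of re-testing in IV.f) as one episode. Add the percentage of patients with at least one episode. Express hyperglycemia per patient in the same way, from scheduled readings.

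**Section VII.** For episode counts, specify negative binomial or Poisson regression with a log patient-days offset and robust variance.

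**Blood glucose monitoring paragraphs.** Reconcile the Group 1 and Group 2 wording so that the same set of scheduled readings is analysed in both arms.

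**Optional.** Compute mean daily BG from scheduled readings only; under the assumptions above this is worth less than 1 mg/dL at arm level.

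**Cost.** Changes of wording, plus the work of flagging scheduled against unscheduled readings. The documents say that readings are recorded in the chart flow-sheet but not that they are time-stamped, so the sponsor should confirm that the flagging and the episode rule can be applied.
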